3.2 Secondary

- 1) **Pain Relief at 2 hours** post-dose, will be assessed using the number of subjects that report a pain level of moderate or severe at baseline and then report a pain level of none or mild at two hours post-dose.
 - 2) The proportion of subjects able to **function normally, at 2 hours** post-dose, will be assessed using the number of subjects that self-report as “normal” on the Functional Disability scale.
 - 3) **Sustained pain relief, from 2 to 24 hours** will be assessed using the number of subjects that do not use any rescue medications, and do not experience any moderate or severe headache pain through the time period of interest.
 - 4) **Sustained freedom from the most bothersome symptom, from 2 to 24 hours**, will be assessed using the number of subjects that do not experience their most bothersome symptom through the time period of interest.
 - 5) The **probability of requiring rescue medication** will be assessed using the number of subjects that take rescue medication within 24 after administration of study medication (rimegepant or placebo).
 - 6) **Sustained ability to function at a normal level, from 2 to 24 hours**, will be assessed using the number of subjects that self-report as “normal” on the Functional Disability scale through the time period of interest.
-

- 7) **Sustained pain relief from 2 to 48 hours**, will be assessed using the number of subjects that do not use any rescue medications, and do not experience any moderate or severe headache pain through the time period of interest.
 - 8) **Sustained freedom from the most bothersome symptom, from 2 to 48 hours**, will be assessed using the number of subjects that do not experience their most bothersome symptom through the time period of interest.
 - 9) **Sustained ability to function at a normal level, from 2 to 48 hours**, will be assessed using the number of subjects that self-report as “normal” on the **functional disability** scale through the time period of interest.
 - 10) **Freedom from photophobia** will be assessed by tabulating the number of subjects that report the absence of photophobia at 2 hours post-dose in the subset of subjects that reported the presence of photophobia at headache baseline.
 - 11) The proportion of subjects able to **function normally, at 90 minutes** post-dose, will be assessed using the number of subjects that self-report as “normal” on the functional disability scale.

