2.3 Study Estimands

The tables that follow lay out the estimands corresponding to the study objectives. In these tables, the following abbreviations are used to describe the handling of intercurrent events for efficacy estimands:

NC=F: Non-Completers = Failure.

A subject with any missing data for an endpoint is classified as a treatment failure.

NC1=F: Non-Completers with more than 1 missing data point = Failure.

Subjects with more than 1 missing data point, other than at the 2, 24 or 48 hour data points, are classified as treatment failures. This applies to endpoints that are based on data from multiple time points. For example, for the durability endpoint of sustained pain freedom from 2 to 24 hours, the subjects should provide data at 2, 3, 4, 6, 8, and 24 hours. For NC1=F imputation, the data at 2 and 24 hour time points must be present or the subject is classified as a failure. However, any single data point may be missing at 3, 4, 6 or 8 hours without penalty. For

sustained pain freedom from 2 to 48 hours, the data at 2, 24, and 48 hours are required to be present.

RM=F: Rescue Medication = Failure.

Subjects that take rescue medication before, or at, the time of the event of interest are classified as failures. If the time of rescue medication is missing, all events on or after the date of rescue medication are classified as failures.

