2.3.2 Secondary Estimands

The estimands corresponding to the secondary objectives are shown in [Table 2](#).

The population summary for all secondary estimands is the difference in the percentage of subjects with a positive result (‘risk difference’) between the BHV-3000 and the Placebo treatment groups.

Table 2: Estimands for the Secondary Objectives

Objective	Pain Relief (at 60 minutes, 90 minutes, or 2 hours)
Population	mITT
Variable	Percent of subjects who report mild or no pain at the specified timepoint
Intercurrent Events	NC=F; RM=F
Objective	Functional Disability (at 60 minutes, 90 minutes, or 2 hours)
Population	mITT
Variable	Percent of subjects with a response of “normal” at the specified timepoint
Intercurrent Events	NC=F; RM=F
Objective	Sustained Pain Relief (2 to 24 hours; or 2 to 48 hours)
Population	mITT
Variable	Percent of subjects who report no pain or mild pain during the period of interest
Intercurrent Events	NC1=F; RM=F
Objective	Sustained Freedom from MBS (2 to 24 hours; or 2 to 48 hours)
Population	mITT
Variable	Percent of subjects who report freedom from MBS during the period of interest
Intercurrent Events	NC1=F; RM=F
Objective	Probability of Rescue Medication within 24 hours post-dose
Population	mITT
Variable	Percent of subjects taking rescue medication within 24 hours post-dose
Intercurrent Events	None
Objective	Sustained Normal Functioning (2 to 24 hours; or 2 to 48 hours)
Population	mITT
Variable	Percent of subjects who report normal functioning on the FDS during the period of interest
Intercurrent Events	NC1=F; RM=F
Objective	Photophobia Freedom at 2 hours post-dose
Population	mITT subjects with photophobia reported as present at migraine onset
Variable	Percent of subjects reporting no photophobia at 2 hours post-dose
Intercurrent Events	NC=F; RM=F
Objective	Sustained Pain Freedom (2 to 24 hours; or 2 to 48 hours)
Population	mITT
Variable	Percent of subjects who report no pain during the period of interest
Intercurrent Events	NC1=F; RM=F
Objective	MBS Freedom at 90 minutes post-dose
Population	mITT subjects
Variable	Percent of subjects reporting freedom from MBS at 90 minutes post-dose
Intercurrent Events	NC=F; RM=F
Objective	Pain Freedom at 90 minutes post-dose
Population	mITT
Variable	Percent of subjects who report no pain at 90 minutes post-dose
Intercurrent Events	NC=F; RM=F
Objective	Phonophobia Freedom at 2 hours post-dose
Population	mITT subjects with phonophobia reported as present at migraine onset

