3 SUBJECT POPULATIONS

3.1 Population Definitions

The following subject populations will be evaluated and used for presentation and analysis of the data:

Enrolled subjects: subjects who sign an informed consent form and are assigned a subject identification number.

Randomized subjects: enrolled subjects who receive a randomization treatment assignment from the interactive web response system (IWRS).

Treated subjects: enrolled subjects who take any amount of study therapy (rimegepant or placebo).

Modified Intent-to-Treat (mITT) subjects: enrolled subjects who are randomized only once, take study therapy, have a baseline migraine of moderate to severe intensity, and who provide at least one post-baseline efficacy data point.

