4.2.5 Multiple Comparisons

Type I error is controlled in this study by using a hierarchical gate-keeping procedure. First, the family of two co-primary endpoints is tested. If the co-primary endpoints are both found to be significant, then secondary endpoints are tested in a fixed sequence. In particular, each co-primary endpoint will be tested for superiority to placebo at a two-sided alpha level of 0.05 without further adjustment for multiplicity. If the primary endpoint tests are both significant, then the following secondary endpoints will be tested in a fixed sequence, in the order shown, with each test conducted at $p=0.05$:

1. Pain Relief at 2 hours
2. Functional Disability at 2 hours
3. Sustained Pain Relief from 2 to 24 hours
4. Sustained Freedom from MBS from 2 to 24 hours
5. Probability of Rescue Medication within 24 hours
6. Sustained Normal Functioning (on FDS) from 2 to 24 hours
7. Sustained Pain Relief from 2 to 48 hours
8. Sustained Freedom from MBS from 2 to 48 hours
9. Sustained Normal Functioning (on FDS) from 2 to 48 hours
10. Freedom from Photophobia at 2 hours

11. Functional Disability at 90 minutes
12. Pain Relief at 90 minutes
13. Sustained Pain Freedom from 2 to 24 hours
14. MBS Freedom at 90 minutes
15. Pain Freedom at 90 minutes
16. Freedom from Phonophobia at 2 hours
17. Sustained Pain Freedom from 2 to 48 hours
18. Pain Relief at 60 minutes
19. Functional Disability at 60 minutes
20. Freedom from Nausea at 2 hours
21. Pain Relapse from 2 to 48 hours

If a test in the hierarchy is not significant, then any further tests on endpoints in the sequence will have p-values presented only for descriptive purposes, and no conclusions will be drawn from those results.

For exploratory endpoints, no attempt will be made to adjust for multiplicity. Any exploratory endpoints for which p-values are produced will be evaluated at an unadjusted two-sided alpha level of 0.05 and presented only for descriptive purposes.

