4.7.4.2 Pain Relief (at 60 Minutes; at 90 Minutes; at 2 Hours)

Pain relief at the specified timepoint post-dose is assessed by tabulating the number of mITT subjects that report a pain level of none or mild (responses of 0 or 1 on the 4-point Likert scale) at the specified timepoint post-dose, by treatment group. Subjects with missing data at the specified timepoint post-dose will be imputed as failures (NC=F).

The results to be presented for the analysis include those described in items (a) through (e) for the primary analysis of pain freedom ([Section 4.7.3.1](#)). In this case, the “risk” is the probability of pain relief at the specified timepoint post-dose.

4.7.4.3 *Probability of Requiring Rescue Medication within 24 Hours*

Whether or not a subject took rescue medication within 24 hours after the initial dose of study medication is tabulated by treatment group using mITT subjects, and the percentages are compared between treatment groups.

The results are presented for the analysis include those described in items (a) through (e) for the primary analysis of pain freedom ([Section 4.7.3.1](#)). In this case, the “risk” is the probability of not requiring rescue medication within 24 hours post-dose.

Information regarding the rescue medication, including the type, date and time taken, dose, route and form of administration, and frequency, is presented in a listing by subject and treatment group.

4.7.4.4 *Functional Disability Scale (at 60 Minutes; at 90 Minutes; at 2 Hours)*

Impact of treatment on subject disability is assessed using a single-question, FDS. Subjects rate the level of disability they perceive as a result of their migraine in performing normal actions using a 4-point scale: Normal Function, Mild Impairment, Severe Impairment, or Required Bedrest. The proportion of mITT subjects who have a response of “normal” at the specified timepoint post dose will be evaluated as the endpoint of interest.

The information from the 4-point scale will be directly summarized as follows:

A table showing descriptive statistics for the 4-point scale, which includes the number and percentage of subjects reporting each of the 4 disability levels at the specified timepoint post-dose, and the percentage of subjects with missing data, for each treatment group, using the observed data. The table will include exact (Clopper-Pearson) 95% CIs for each percentage.

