4.7.4.11 Sustained Normal Functioning from 2 to 24 Hours

Sustained normal functioning is assessed using the number of mITT subjects that experienced normal functioning on the FDS at all time points from 2 through 24 hours post-dose. Subjects with missing FDS scores at 1 or fewer time points, given that they have responses of normal at all other time points including the 2 and 24 hour post-dose time points will be considered as successes. Subjects with responses missing at greater than 1 post-dose time point, missing data at the 2 or 24 hour time point, or with any report of non-normal functioning will be considered as failures.

The results to be presented for the analysis include those described in items (a) through (e) for the primary analysis of pain freedom ([Section 4.7.3.1](#)). In this case, the “risk” is the probability of sustained normal functioning from 2 to 24 hours.

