2.2 Time to First Report of Absence of Various Symptoms

For each of the following variables, two sets of Kaplan-Meier plots and tables were created:

- Time to First Report of Absence of Most Bothersome Symptom
- Time to First Report of Absence of Nausea
- Time to First Report of Absence of Photophobia
- Time to First Report of Absence of Phonophobia
- Time to First Report of Return to Normal Functioning

The first set of plots and tables was similar to those created for the time to rescue medication (using actual time). For the second set of plots, nominal (planned time point) as opposed to actual time was used for clinical event times. Censoring was measured using actual time as in all previous plots.

For both sets of analyses, the analysis population for MBS was the set of mITT subjects. The analysis population for nausea, phonophobia, and photophobia was the subset of mITT subjects that reported the symptom as present at the onset of their study migraine. The analysis population for functional disability was the subset of mITT subjects that reported abnormal functioning at the onset of their study migraine. The y-axis for all plots represents the probability of the occurrence of the event of interest, and therefore are increasing from left to right.

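### Should the five functional-disability endpoints leave out subjects who already function normally at migraine onset?

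*SAP*

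**What the plan says.** SAP 4.2.5 places FDS endpoints at positions 2 (2 hours), 6 (sustained, 2 to 24 hours), 9 (sustained, 2 to 48 hours), 11 (90 minutes) and 19 (60 minutes). Once a test in the sequence fails, later ones "will have p-values presented only for descriptive purposes, and no conclusions will be drawn from those results".

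SAP Table 2 gives mITT as the population for all five. Section 4.7.4.4 counts "The proportion of mITT subjects who have a response of" normal. Section 4.7.4.11 reads "Sustained normal functioning is assessed using the number of mITT subjects that experienced normal functioning on the FDS at all time points" in the window, and 4.7.4.12 does the same to 48 hours. The mITT definition in SAP 3.1 requires that subjects "have a baseline migraine of moderate to severe intensity, and who provide at least one post-baseline efficacy data point"; it does not mention function. Protocol 3.2 defines the 2-hour endpoint in the same way: it "will be assessed using the number of subjects that self-report as" normal.

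Other analyses condition on onset status. The photophobia endpoint in SAP Table 2 uses "mITT subjects with photophobia reported as present at migraine onset", and phonophobia and nausea are handled likewise. For time to return to normal functioning, SAP Appendix 3 section 2.2 states: "The analysis population for functional disability was the subset of mITT subjects that reported abnormal functioning at the onset of their study migraine".

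**The concern.** FDS is recorded at migraine onset (schedule of assessments), so subjects already normal then can be identified, yet they stay in the denominator. They can only remain normal or worsen. If the drug does less in them than in impaired subjects, the pooled risk difference shrinks.

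The plan states power for the co-primary endpoints only, so nothing in it shows that position 2 can absorb such dilution. A miss there would remove 19 later tests from confirmatory standing. The SAP restricts the three symptom endpoints to affected subjects and the time-to-function analysis to impaired subjects, so the FDS endpoints can look like an oversight.

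**Working it through.** **The plan's own figures.** 715 × 0.85 = 607.75, against about 600 treated per arm; 0.95 × 0.95 = 0.9025, against roughly 90% joint power. Both reproduce, the second if the two tests are treated as independent. No FDS power is stated.

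**What the documents supply for FDS.** They give no onset distribution, response rate or effect size. The nearest figure is the background statement in Protocol 1.3 that about 80% of people cannot work or function normally during an attack. That points to about 20% as a ceiling for the share normal at onset; treated attacks of moderate or severe pain probably have fewer.

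**Assumed inputs.** 600 per arm, two-sided 0.05, unpooled z test, no stratification.
- f, share normal at onset: 5, 10 or 20%
- p0, placebo rate of normal function at 2 hours among impaired subjects: 20 or 25%
- d, drug effect in impaired subjects: 8 to 12 points
- s, placebo rate of staying normal among those normal at onset: 70 or 85%
- e, drug effect in those subjects: 0, d/2 or d

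**Formulas.** Restricted analysis: n = 600(1 − f) per arm, rates p0 and p0 + d. Full mITT: n = 600 per arm, placebo rate (1 − f)p0 + f·s, active rate (1 − f)(p0 + d) + f(s + e). The full-set difference is (1 − f)d + f·e. Power = Φ(difference/SE − 1.96).

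**One case in full:** f = 0.10, p0 = 0.25, d = 0.10, s = 0.70.
- Restricted: n = 540; SE = √[(0.35·0.65 + 0.25·0.75)/540] = 0.0277; z = 3.61; power 95.0%.
- Full set, e = 0: rates 0.295 and 0.385; SE = √[(0.295·0.705 + 0.385·0.615)/600] = 0.0272; z = 3.31; power 91.1%, a loss of 3.9 points.
- Full set, e = 0.05: rates 0.295 and 0.390; z = 3.48; power 93.6%, a loss of 1.4 points.
- Full set, e = 0.10: rates 0.295 and 0.395; z = 3.66; power 95.6%, a gain of 0.6 points.

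**Power lost by using all mITT, in points, with no drug effect in subjects normal at onset (e = 0):**

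| Share normal at onset | d = 8 points | d = 10 points | d = 12 points |
|---|---|---|---|
| 5% | 3.4–4.3 | 1.5–1.8 | 0.3–0.5 |
| 10% | 7.1–9.3 | 3.9–4.5 | 1.1–1.6 |
| 20% | 15.0–19.3 | 10.8–12.8 | 5.1–5.9 |

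At 2 to 3% normal, the loss is 0.5–1.0 points for d = 10 and 1.3–2.5 for d = 8.

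With half the effect (e = d/2), the loss is 2.8–5.1 points at 10% normal and d = 8, 1.4–2.2 at 10% and d = 10, and 5.0–9.2 at 20% and d = 8. With equal effect (e = d), results over the 5 to 20% grid run from a 1.5-point loss to a 3.4-point gain for the full set. At 10% normal and d = 10, the loss disappears once e reaches 8.4 to 11.9 points, that is, when the drug preserves function about as well as it restores it.

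**Is the denominator a slip?** Three comparisons say not.
- The objective (Protocol 2.2 and SAP 1.2.2, item 2) is the ability to function normally at 2 hours, which is a state and not a change from onset.
- Protocol 3.2 writes an affected-at-onset subset into the photophobia, phonophobia and nausea items and into none of the FDS items. SAP Table 2, 4.7.4.4, 4.7.4.11 and 4.7.4.12 follow it, as do the binary FDS analyses in Appendix 3 sections 1, 1.4 and 4.3.
- The restriction in Appendix 3 section 2.2 follows from its event. Nobody already functioning normally can return to normal.

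Subjects normal at onset are not automatic successes either. They must report normal again with the required data present, and under SAP 2.3 "Subjects that take rescue medication before, or at, the time of the event of interest are classified as failures".

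**The case for a change.** The best case for restricting is that FDS stands apart among the gated improvement endpoints. Pain endpoints are conditioned on baseline pain through mITT itself. The MBS is named at onset, and the primary estimand counts failure to name one as failure. The other three symptoms are limited to affected subjects. Only FDS accepts a good status at follow-up without asking whether it was poor at the start, and the SAP gives no reason. The filter would use data already collected, and position 2 guards 19 further tests.

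The asymmetry is real and unexplained, and a conditional loss of power is possible. It does not follow that the five endpoints should be re-based. Freedom from a symptom presupposes the symptom; functioning normally does not presuppose impairment. Staying functional through a moderate or severe attack is a benefit that the restricted version would drop from the claim. The restriction would also be more than a wording edit: Protocol section 11 requires an amendment with IRB/IEC approval. SAP 4.9.1 provides for subjects who dose before giving baseline migraine characteristics, so a safe filter would have to keep those without a pre-dose rating and would mix two kinds of subject.

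One drafting ambiguity also stands. SAP 4.7.5.5 lists FDS first among outcomes tabulated in mITT subjects, then among symptoms expressed as a percentage of those reporting them at baseline. It concerns exploratory tabulations only, and the analyst can settle it by following the mITT definition used for FDS elsewhere.

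**Conclusion.** No change follows. Analysing FDS in all mITT subjects is a valid and consistently stated estimand. It leaves type I error, the randomised comparison, both co-primary endpoints and the first secondary test untouched.

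The possible cost is power at position 2. It is under 5 points if at most 10% are normal at onset and the effect in impaired subjects is at least 10 points. Losses of about 13 to 19 points need 20% normal, an 8 to 9 point effect and no benefit in subjects normal at onset, all together. If those subjects benefit equally, restricting would cost up to 3.4 points in some settings and gain at most 1.5 in others, so even the direction is not settled by the documents. These figures rest wholly on assumed onset shares, rates and effects. They were worked out for the 2-hour endpoint only; the other four share the structure but were not computed.

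An onset FDS count by arm, or a restricted analysis labelled supportive, would help a reader of the report. Neither would alter any result or conclusion that the plan provides for.

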4.7.4.6 Sustained Pain Freedom from 2 to 48 Hours

Sustained pain freedom is assessed using the number of mITT subjects that experienced no headache pain (response of 0 on Likert scale) at all time points from 2 through 48 hours post-dose. Subjects with missing pain scores at no more than 1 time point, given that they have responses of no pain (response of 0 on Likert scale) at the 2, 24, and 48 hour time points will be considered as successes. Subjects with responses missing at greater than 1 time point; missing data at the 2, 24, or 48 hour time point; or with any pain score greater than 0 will be considered as failures.

The results to be presented for the analysis include those described in items (a) through (e) for the primary analysis of pain freedom ([Section 4.7.3.1](#)). In this case, the “risk” is the probability of sustained pain freedom from 2 to 48 hours.

4.7.4.7 Sustained Pain Relief from 2 to 24 Hours

Sustained pain relief is assessed using the number of mITT subjects who experience no or mild headache pain (responses of either 0 or 1 on 4-point Likert scale) at all time points from 2 through 24 hours post-dose. Subjects with missing pain scores at no more than 1 time point, given that they have responses of no or mild pain at the 2 and 24 hour time points will be considered as successes. Subjects with responses missing at more than 1 time point, with missing data at the 2 or 24 hour time points, or with any pain score greater than 1 will be considered as failures.

The results to be presented for the analysis include those described in items (a) through (e) for the primary analysis of pain freedom ([Section 4.7.3.1](#)). In this case, the “risk” is the probability of sustained pain relief from 2 to 24 hours.

4.7.4.8 Sustained Pain Relief from 2 to 48 Hours

Sustained pain relief will be assessed using the number of subjects that experience no or mild headache pain (response of 0 or 1 on the 4-point Likert scale) at all time points from 2 through 48 hours post-dose. Subjects with missing pain scores at no more than 1 time point, given that they have responses of no or mild pain at all other time points including the 2, 24, and 48 hour time points will be considered as successes. Subjects with responses missing at more than 1 time point; with missing data at the 2, 24, or 48 hour time point; or with any pain score greater than 1 will be considered as failures.

The results to be presented for the analysis include those described in items (a) through (e) for the primary analysis of pain freedom ([Section 4.7.3.1](#)). In this case, the “risk” is the probability of sustained pain relief from 2 to 48 hours.

